3.3 Rationale for study design

The study design follows the FDA recommendations on simulated use validation study design as described in the FDA guidance ‘Applying Human Factors and Usability Engineering to Medical Devices’ (FDA 2016). As per FDA guidance, this HF study intends to enroll sufficient patients to have a total of 45 subjects completing the study, with approximately 15 subjects in each of the three age groups: 6-10 years, 11-17 years, and ≥ 18 years. In order to minimize bias,

only CF patients and caregivers naïve to the use of the Podhaler device will be enrolled. These subjects will not be trained prior to using TOBI Podhaler. Placebo capsules instead of active drug will be used to mimic the real life self-administration of the active drug. Subjects will be observed during dosing and will be subsequently interviewed after completing the dose.

3.4 Rationale for dose/regimen, route of administration and duration of treatment

The use of placebo capsules instead of active TIP capsules should shorten the recruitment period by allowing enrollment of a broader range of TOBI Podhaler-naïve CF patients, including those who may be currently taking other inhalational treatments, or those who do not have a positive culture for *P. aeruginosa*. Also it allows for a flexible scheduling of subject's study visit day, independent of the subject's treatment. This is important as it will allow having a HF specialist at the site to observe the use, conduct post-dose discussions including root cause analysis of errors and collect subjective feedback. Involvement of this HF specialist in all study assessment sessions will ensure consistency.

3.5 Rationale for choice of comparator

Not applicable.

3.6 Purpose and timing of interim analyses/design adaptations

Not applicable.

3.7 Risks and benefits

Besides contributing to the assessment of the user interface that could be of benefit to patients, this trial may not offer a direct benefit to the subjects. Any risk to subjects in this trial will be minimized by compliance with the inclusion/exclusion criteria. No active drug is being administered but there is a potential risk of an allergic reaction from unrecognized sensitization to the placebo content (i.e. DSPC (1, 2-distearoyl-sn-glycero-3-phosphocholine) and/or calcium chloride).

As with all inhaled medications, cough and bronchospasm (asymptomatic or reported as wheeze) may occur; especially in subjects with known or suspected bronchial hyper-responsiveness.

Patients who experience any of these symptoms after dosing should be managed as per standard of care and the events should be recorded as Adverse Events (AEs).

Subjects will also be asked not to continue with any activity that they find painful. If bodily fluid is drawn or expelled, the HF Interviewer and Investigator/designated staff will quarantine the Podhaler device and anything that could have come into contact with the bodily fluid. The room will be sanitized and the subject will be treated as per the investigator decision. All AEs must be recorded on the appropriate CRF capturing AEs.

3.7.1 Low risks

- It is possible that the subjects may attempt to swallow a capsule.

Mitigation: the HF Interviewer and HF Observer will be trained to prevent subjects from swallowing capsules as far as possible along with any other potentially hazardous activity involving their interaction with the Podhaler device. Any attempts to swallow a capsule will be appropriately recorded by the HF Interviewer and HF Observer.

- It is possible that small fragments of the capsule can get into the user's mouth or throat after inhalation – this may disconcert the subject but is not harmful as the capsule material is pharmaceutical grade, manufactured under Current Good Manufacturing Practice (cGMP) and the capsule material is otherwise used for oral ingestion.

Mitigation: Subjects who express any concern after inhalation will be informed that they may feel a slight sensation of capsule fragments in the back of their throat and that these small pieces will not hurt them if swallowed or inhaled (per PIL).

3.7.2 Medium risks:

- It is important to keep CF patients away from one another to avoid cross-contamination and shared infections.

Mitigation: where subjects are seen in a clinical/research facility, assessment sessions will be arranged so that individuals are not waiting in a room together. The interview room table tops and chairs will be sanitized as per the site's hygiene protocols. The HF Interviewer and HF Observer will sanitize his/her hands between sessions. CF patients will only be allowed to touch the materials that they will be using in the study. Other monthly packs will be stored outside the interview room and in a place where subjects will not enter.

- It is possible that the subject will put the capsule into the device without removing the mouthpiece first, and could inhale the whole capsule; it is also possible that the subject will put the capsule into the device and neglect to replace the mouthpiece before inhaling, and could inhale the whole capsule.

Mitigation: the HF Interviewer and/or HF Observer will be instructed to intervene immediately if they see that subjects have placed the capsule into the device without removing or replacing the mouthpiece and are about to inhale a capsule. This will be appropriately recorded by the HF Interviewer and HF Observer if it occurs.

4 Population

Males and females aged 6 years and older with a diagnosis of CF and with a forced expiratory volume in one second (FEV₁) of at least 25% of normal predicted values for age, sex, and height are eligible for inclusion into this study. It is estimated that about 50 subjects will be enrolled with the aim of having 45 CF subjects completing the study. These completers will be divided among three age groups: 6-10, 11-17 and ≥ 18 years (approximately 15 subjects per age group). Subjects and caregivers should have no previous experience with the use of the Podhaler device.

4.1 Inclusion criteria

Subjects eligible for inclusion in this study must fulfill all of the following criteria:

1. Written informed consent or, parent/guardian consent and where applicable pediatric assent, must be obtained before any assessment is performed.
2. Male and female subjects aged 6 years and older.
3. Confirmed diagnosis of CF by one or more of the following tests for CF as documented in the patient's medical history :
 - quantitative pilocarpine iontophoresis sweat chloride test of > 60 mmol/L or 60 mEq/L
 - genotype with identifiable CF-causing mutations on both chromosomes,
 - an abnormal nasal transepithelial potential difference characteristic of CF
4. FEV₁ value must be at least 25% of normal predicted values for age, sex, and height as documented in the patient's medical history (historical values within 3 months can be used for this criterion).
5. Able to comply with all protocol requirements.
6. Clinically stable in the opinion of the investigator.

4.2 Exclusion criteria

Subjects fulfilling any of the following criteria are not eligible for inclusion in this study. No additional exclusions may be applied by the investigator, in order to ensure that the study population will be representative of all eligible subjects.

1. Subjects currently enrolled in studies that are not considered as observational non-investigational studies.
2. If the subject or caregiver has used the Podhaler device previously.
3. Hemoptysis more than approximately 60 mL at any time within 30 days prior to enrollment.
4. History of hypersensitivity to the inhaled placebo dry powder (DSPC and/or calcium chloride powder).
5. Signs and symptoms of acute pulmonary disease, e.g. pneumonia, pneumothorax, bronchospasm, acute respiratory infection.
6. Clinically significant conditions or findings at enrollment that might interfere with the accurate and valid assessment of this study.
7. Subjects or caregivers who are considered potentially unreliable or considered unlikely to be compliant within the trial.
8. Pregnant women.

5 Treatment

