2.1 Objectives and related endpoints

Table 2-1 Objectives and related endpoints

Objective(s)	Endpoint(s)
Primary Objective(s) 
To evaluate whether the user interface of TOBI Podhaler can support safe and effective use for patients with CF	Endpoint(s) for primary objective(s) 
Use errors and close calls associated with the simulated inhalation of one dose using TOBI Podhaler
Secondary Objective(s) 
Not applicable	Endpoint(s) for secondary objective(s) 
Not applicable
Exploratory Objective(s) 
Not applicable	Endpoint(s) for exploratory objective(s) 
Not applicable

3 Investigational plan

[figure not shown]

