5.6.2 Discontinuation of study treatment

Discontinuation of study treatment for a patient occurs when study drug is stopped earlier than the protocol planned duration, and can be initiated by either the patient or the investigator. In this single visit study, discontinuation will occur if the subject does not complete the inhalation of the 4 placebo capsules and/or the HF interview.

The investigator must discontinue study treatment for a given patient if, on balance, he/she believes that continuation would negatively impact the risk/benefit of trial participation. Study treatment must be discontinued under the following circumstances:

- Patient wish
- Any situation in which study participation might result in a safety risk to the patient
- Non-compliance of the subject with study procedures or investigator instructions, as per the investigator's judgment
- Emergence of Adverse Events (AE) when worsened from study entry or any newly occurring development of AEs
- Any other protocol deviation that results in a significant risk to the subject's safety

Subjects who are prematurely withdrawn from the study will be replaced by an equal number of newly enrolled subjects to meet the intended target of 15 subjects in each of the three age categories i.e., 45 completed subjects. However, premature withdrawal does not necessarily mean that the subject has failed to complete the HF assessment. It is possible in certain circumstances that subjects could demonstrate the ability to use TOBI Podhaler and carry out the dosing task without using all four capsules; for example, a 6 year-old child may not demonstrate sufficient attention or patience for the entire dose to be taken.

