6.5 Human factors assessment

The HF assessment is summarized in [Section 3.2](#) and detailed in [Appendix 1](#) and includes the following:

- An interview guide will provide a script for the HF Interviewer ([Appendix 4](#)).
- HF assessment checklist will be a paper form completed both by a qualified trained Interviewer from a specialized HF vendor and by the trained HF Observer. Data capture by two independent assessors will help to ensure accurate and unbiased recording. The checklist is used to collect all of the information required for data analysis on observed performance of use steps and response to comprehension questions. Demographic variables include but are not limited to subject age, gender, previous inhalation device experience, dominant hand, vision and dexterity challenges, health literacy (US school reading grade equivalent), educational attainment, and assistance provided to minors by caregivers during the study. Observed data collected for subject performance of use steps will be marked as pass or fail. Evident close calls will also be noted down. Key points from Interviewer-led discussion will be noted down on the HF Assessment checklists (e.g. observations, opinions of the subject etc.) – with the objective of capturing root cause of use errors and/or subject misunderstandings.
 - HF Assessment sessions will be digitally recorded in audio and video for future reference, and to allow independent checking of study data.
 - The used capsules (including photos) and Podhaler device(s) (if device(s) seem to be defective) will be subject to post-use inspection by the HF Interviewer in order to inform discussion on errors and their root cause.

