13.5.2 Summary of TOBI Podhaler IFU validation study CTBM100C2412

The IFU validation study was conducted in 2014-2015 in the US with 45 CF patients, accompanied by caregivers where the patient was aged 17 years or less. The study was conducted to meet the following PMR 1928-3: “An actual use human factors study to validate the approved IFU. The study will enroll 45 subjects in total with three age groups of approximately 15 subjects each: 6- 10 years, 11-17 years, and > 18 years. Only CF patients naïve to use of the Podhaler device will be enrolled. These subjects will not be trained prior to reading the IFU and will be observed during the study.”

The study showed that the majority of CF patients and/or their caregivers can understand and follow the approved IFU without prior training. All patients understood the basic sequence of operation of the Podhaler device: load, pierce and inhale.

Patients were asked to take one dose. Of the 45 patients, 31 patients emptied the powder from all 4 capsules completely. Of the 14 patients who did not completely empty the powder from all 4 capsules, 4 patients cleared more than $\frac{3}{4}$ of the total powder and 6/14 patients cleared approximately $\frac{3}{4}$; 4/14 patients cleared less than $\frac{3}{4}$ of the total powder.

Six of the 14 patients who did not empty the capsules failed for reasons which are not attributable to the IFU, such as failure to engage with the IFU or failure of the caregiver to understand that a child was not inhaling.

However, 8 of the 14 patients who did not empty the capsules failed because, following incorrect inhalation technique or piercing error, they did not understand the checking procedure outlined in IFU step 17 – in particular, what a correctly emptied capsule should look like.

Moreover, from observation some patients found this step difficult to navigate and understand and 10/45 patients mentioned confusion or difficulty around checking capsules in post-use discussion.

Misunderstanding the recommendation to inhale twice from each capsule was a contributory cause of failure in 4 cases, although it is evidently possible for some patients to empty the capsules with only one inhalation. 8/45 mentioned confusion or difficulty with the repeat inhalation step.

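### Exclusion 7 lets an undefined judgement of reliability or compliance remove users from a study that measures use errors; it and inclusion 5 should be narrowed

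*Protocol*

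**What the plan says.** Exclusion 7 in Protocol 4.2 covers "Subjects or caregivers who are considered potentially unreliable or considered unlikely to be compliant within the trial". It gives no definition, threshold or assessor. Protocol 5.3 has the investigator or a delegate confirm eligibility, so the judgement presumably falls to the site. The lead-in to the same list says "No additional exclusions may be applied by the investigator, in order to ensure that the study population will be representative of all eligible subjects".

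Inclusion 5 in Protocol 4.1 adds a similar requirement, "Able to comply with all protocol requirements", also without definition.

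The endpoint in Protocol Table 2-1 is "Use errors and close calls associated with the simulated inhalation of one dose using TOBI Podhaler". Protocol 6.5 says how it is scored: "Observed data collected for subject performance of use steps will be marked as pass or fail". Users receive the commercial pack and no training (Protocol 3.1, 3.2). The post-marketing requirement quoted in Protocol 1.1 concerns the intended users of the product.

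There is no hypothesis test (Protocol 9.4.2). The analysis is mainly qualitative, by root cause (Protocol 9.4), and ends in a judgement on whether the findings validate the interface (Protocol 13.12). About 15 completers are planned in each of three age groups (Protocol 9.8).

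Protocol 6.1 collects inclusion and exclusion data on screening failures, and SAP 2.3 reports the reasons for screen failure.

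**The concern.** A human factors validation study learns from the errors it sees. If people expected to be careless, disengaged or poor at following directions can be turned away at screening, the sample leans towards users who will do well, while the product will be prescribed to both kinds. An undefined criterion also lets sites apply different standards, and nothing in the text stops a site from using its impression of how well a family would cope with the leaflet.

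The design gives little reason for a broad reliability screen. It is one visit with a session of about 60 minutes (Protocol 3.1), and loss to follow-up is not applicable (Protocol 5.6.4). Inclusion 6 and exclusions 3 to 6 already deal with clinical fitness.

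At stake is whether a failure mode appears at all. With about 15 users per group, losing a few error-prone ones can mean that a type of error is never observed, never discussed in the interview and never traced to its root cause. Listing the reasons for screen failure shows that people were excluded. It cannot recover the errors they would have made.

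**Working it through.** **1. The plan's own figure.** 3 groups × 15 = 45 completers. About 50 enrolled implies a loss of 1 − 45/50 = 10%, and 45/0.90 = 50. Both figures reproduce. Exclusion 7 plays no part in them, and no error-rate target or power statement exists against which to test it.

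**2. Does any text narrow the criterion?** The second half of exclusion 7 speaks of compliance within the trial, which could mean trial procedures only, but nothing says so. The first half, on potential unreliability, has no object at all. No other section of the Protocol or SAP supplies one.

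**3. Do the documents link this trait to error?** Yes, in two places.
- Protocol 13.5.1 (2011 study): failure to invert the inhaler went from 20/62 (32.3%) to 15/35 (43%), and failure to check capsules from 20/62 (32.3%) to 17/34 (50%). Both are said to suggest non-compliance, with a study artifact as a possible or probable explanation.
- Protocol 13.5.2 (study CTBM100C2412): 14 of 45 did not empty all four capsules. Six of the 14 failed for reasons not attributed to the IFU, "such as failure to engage with the IFU or failure of the caregiver to understand that a child was not inhaling".

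**4. Illustration from study CTBM100C2412.** Suppose a filter had removed k of those six failures, no successes, and nobody had been replaced. The rate is (14 − k)/(45 − k).

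| k | Rate of not emptying all capsules |
|---|---|
| 0 | 14/45 = 31.1% |
| 1 | 13/44 = 29.5% |
| 3 | 11/42 = 26.2% |
| 6 | 8/39 = 20.5% |

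Two checks limit this table.
- It assumes a filter that picks out only failures. If six people were removed and three of them were successes, the rate would be 11/39 = 28.2%.
- The six are the failures not attributed to the IFU. Removing all six leaves the eight IFU-attributed failures in place, and their share rises from 8/45 = 17.8% to 8/39 = 20.5%.

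**5. General range (assumed inputs).** Let s be the share of otherwise eligible users excluded, RR their error risk relative to those kept, and p the rate among those kept. The rate in all eligible users is (1 − s)p + s·RR·p = p[1 + s(RR − 1)]. The relative shortfall of the observed rate is 1 − 1/[1 + s(RR − 1)]. The documents give neither s nor RR; I take s = 5% to 20% and RR = 1 to 3.

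| s | RR | Observed p | Rate in all eligible | Shortfall |
|---|---|---|---|---|
| any | 1 | any | same as p | 0% |
| 10% | 2 | 10% | 11.0% | 9.1% |
| 20% | 3 | 5% | 7.0% | 28.6% |

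The chance of seeing at least one such error among n users is 1 − (1 − rate)^n. In the last row, moving from 7% to 5% lowers it from 66.3% to 53.7% for n = 15, and from 96.2% to 90.1% for n = 45.

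**The case against.** The best defence is that exclusion 7 concerns cooperation with the trial, and that even a one-visit study needs it. Device naivety is self-confirmed (Protocol 3.1). Root cause depends on candid interview answers (Protocol 3.2.2). Participants must treat a placebo session as real dosing (Appendix 4), and staff may have to step in before a capsule is inhaled (Protocol 3.7.2). That need is genuine and the fix keeps it. It does not justify wording that reaches further.

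Second, no decision rests on a rate, and some safeguards exist: reasons for screen failure are reported, and Amendment 01 removed the minimum literacy score. This stands as a limit on the consequences. It does not settle the point, because the final judgement still depends on which errors were observed.

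A reader might infer several stronger things that the documents do not support.
- *That error rates are shown to be biased downwards.* The direction is an inference. It needs those excluded to err more often than those kept.
- *That study CTBM100C2412 measures the effect.* Nothing says that any of the six would have met exclusion 7. The stated reasons are examples without counts, and a caregiver missing that a child was not inhaling could hardly be foreseen at screening. Beyond CF and device naivety, that study's eligibility criteria are not given; if it had a similar exclusion, these failures occurred despite it.
- *That section 4.2 contradicts itself.* The lead-in bars criteria beyond the list, and exclusion 7 is on the list. The aim "in order to ensure that the study population will be representative of all eligible subjects" refers to subjects whom that list defines.
- *That Protocol 5.6.2 repeats the filter.* Its bullet reads "Non-compliance of the subject with study procedures or investigator instructions", which is not the IFU. Sites do not assist with inhalation (Protocol 5.5.4), and the interviewer gives non-leading replies to questions about use (Appendix 4), so a use error is not plainly non-compliance under that rule.

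**Conclusion.** The point holds as a weakness of wording with a plausible effect on the endpoint. Exclusion 7 permits selection on a trait that the documents themselves associate with use error, and no text confines it to trial conduct.

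The conclusion rests on two assumptions: that sites use the criterion at all, and that those excluded would have erred more often. The size is unknown and may be small. Under the assumed range the relative understatement runs from nil to 28.6%, and the change from 31% to 26% or 21% marks a hypothetical upper end. The more practical risk is a failure mode going unseen in a group of about 15. No type I error or sample size figure is affected. The change is worth making because it is cheap and the lost observations cannot be recovered afterwards.

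**What to change.** 1. **Exclusion 7.** Limit it to subjects or caregivers who are unable or unwilling to give consent or assent, to confirm that they have not used the device, or to remain for and cooperate with the single session.
2. **Exclusion 7 and inclusion 5.** State in both that an expectation that someone will not read or follow the IFU, or low health literacy, is not a ground for exclusion. Inclusion 5 must be covered because it permits the same judgement. Naming literacy keeps the REALM-SF result, which is still obtained at screening, from bringing back informally the threshold that Amendment 01 removed.
3. **Screen-failure table (SAP 2.3).** Show the number excluded under each of these two criteria, by age group. The data are already collected, and SAP 2.2.1 already plans age subgroups for all post-text tables.
4. **Optional.** Add a clarification to Protocol 5.6.2 that a use error is not in itself non-compliance with study procedures. The discontinuation rule is otherwise outside this point.

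The cost is two reworded criteria and two table rows. The downside is a few more incomplete sessions, which the replacement rule in Protocol 5.6.2 already covers. The target of 45 completers from about 50 enrolled need not change.
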